Patients will be introduced to and asked to participate in the trial when they arrive to the surgical ward or emergency department by the surgical resident. They will not be subjected to any additional steps other than the standard hospital protocols as our trial begins in the operating room where patients will be randomly allocated into 2 groups: the control group (direct wound closure) and the intervention group (PVI wound wash before closure).

After the operation, patients will be monitored and observed at the hospital by the staff until discharge and will be given a specialized follow-up card. Following discharge, follow-up will be in the form of fixed outpatient clinic visit after the first week postoperatively and continue with phone calls made at regular 1-week intervals inquiring about symptoms and signs of SSI based on a questionnaire guided by the CDC definitions [27]. If a patient displays ≥ 1 symptom listed in the CDC checklist (See appendix 5), he/she will be invited to follow-up in our outpatient clinic and will be identified by their card. This will allow the physician to fill out the data collection form in their files and obtain a picture for documentation purposes. Follow-up will continue for a period of 30 days.

Sample Size

Using PASSII program for sample size calculation and assuming SSI incidence of 10% in control group and 5% in intervention group, setting **power** at 80% and **α -error** at 0.05, sample size of 345 patient for each group will be needed. We plan to enroll an additional 10% of the calculated sample size for each group in anticipation of a loss to follow-up rate of 10%. The total sample size will be **760 patients**.

Assignment of Interventions

Sequence Generation

A statistician not directly involved in the study or analysis will prepare a computer-generated randomization sequence. No blocking will be used. The sequence will be provided to the trialists in the form of serially numbered opaque envelopes containing details of either the intervention or the control and a random identifier.

Enrolment and Allocation Concealment

The patients will be enrolled by the resident doctors and given a study ID number.

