
 • Diagnosis/treatment of cellulitis (redness/warmth/swelling), by itself, does not meet criterion "d" for superficial incisional SSI. Conversely, an incision that is draining or that has organisms identified by culture or non-culture based testing is not considered a cellulitis. • A stitch abscess alone (minimal inflammation and discharge confined to the points of suture penetration). • For an NHSN operative procedure, a laparoscopic trocar site is considered a surgical incision and not a stab wound. • A localized stab wound or pin site infection is not considered an SSI; depending on the depth, these infections might be considered either a skin (SKIN) or soft tissue (ST) infection. 		

January 2021

Surgical Site Infection (SSI)		
Deep incisional SSI (DIP, DIS)		
Element	Element Met	Date
Must meet the following criteria:		
Date of event occurs within 30 or 90 days after the NHSN operative procedure (where day 1 = the procedure date) according to the list in Table 2 (see below)		
AND		
Involves deep soft tissues of the incision (for example, fascial and muscle layers)		
AND Patient has at least one of the following:		
a. Purulent drainage from the deep incision.		
b. A deep incision that spontaneously dehisces, or is deliberately opened or aspirated by a surgeon, physician* or physician designee AND Organism(s) identified from the deep soft tissues of the incision by a culture or non-culture based microbiologic testing method which is performed for purposes of clinical diagnosis or treatment (for example, not Active Surveillance Culture/Testing (ASC/AST)) or culture or non-culture based microbiologic testing method is not performed. A culture or non-culture base test from the deep soft tissues of the incision that has a negative finding does not meet this criterion. AND Patient has at least one of the following signs or symptoms: 
 • Fever (>38°C) • Localized pain or tenderness 		
c. An abscess or other evidence of infection involving the deep incision that is detected on gross anatomical or histopathologic exam, or imaging test.		

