Patient identification details (used locally for follow-up only)		
Patient name:	Study ID:	Phone number:
3) Follow up		

3-1 *Follow up intervals: (Make sure you contact the patient at every interval, then checkmark the interval that the patient develops SSI)
 
 0-7 days  8-14 days  15-21 days  22-28 days  28-30 days
	
3-5 *SSI survey Qs: (check all that apply) Does the patient suffer from....
 
 Pain or tenderness at the surgical site  Swelling at the surgical site  Hotness at the surgical site  Pus draining from the site of incision  Fever postoperatively (degree:)  Surgical incision has been deliberately opened by a physician for signs of infection before due time for stitch removal
 
*if the patient scored 1/6 or more please ask him to directly go to the surgical outpatient clinic to complete the follow up process.
 
*if the patient scored 0/6 please repeat the SSI survey in the mentioned intervals till the end of the 30 days follow up.
	
3-6-1 *Did the patient develop SSI within 30 days postoperatively?
 
 Yes, please specify the postoperative day:  No
 
3-6-2* Was the patient readmitted to the hospital due to SSI?
 
 Yes (for how many days:)  No
 
3-6-3* Did the SSI require another surgical procedure?
 
 Yes (specify:)  No

3-2 *Follow up was done through: (check all that applies)
 
 Inpatient hospital records  Outpatient clinic  Over phone
	
3-7 *Did the patient develop any of the following due to SSI? (check all that apply)
 
 Sepsis  Septic shock  Multiple organ dysfunction syndrome  Wound dehiscence  Others (specify)
	
3-8 *Was there any adverse effect of PVP-I application?
 
 Local skin reaction  Poor wound healing  Other: (please specify:)

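### The trigger for a clinic referral is stated in two conflicting ways: the telephone survey omits redness and spontaneous wound separation, although the text refers on any symptom in the CDC checklist

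*Protocol*

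**What the plan says.** The Participant Timeline section of the protocol sets out follow-up after discharge. Every patient has one scheduled examination: "follow-up will be in the form of fixed outpatient clinic visit after the first week postoperatively". After that, the teams "continue with phone calls made at regular 1-week intervals inquiring about symptoms and signs of SSI". The rule for bringing a patient back is: "If a patient displays ≥ 1 symptom listed in the CDC checklist (See appendix 5), he/she will be invited to follow-up in our outpatient clinic".

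Appendix 5 is the CDC checklist. It lists erythema among the local signs in superficial criterion c. Deep criterion b begins: "A deep incision that spontaneously dehisces, or is deliberately opened or aspirated by a surgeon".

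Appendix 6, item 3-5, is the survey completed at each contact. Its six items are pain or tenderness, swelling, heat ("Hotness at the surgical site"), pus, fever, and "Surgical incision has been deliberately opened by a physician for signs of infection before due time for stitch removal". Its instruction is: "if the patient scored 1/6 or more please ask him to directly go to the surgical outpatient clinic". A patient who scores 0/6 has the survey repeated at the next interval until day 30.

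**The concern.** The two rules cannot both be followed. A patient whose only complaint is a red wound, or a wound that has come apart without pain or fever, has a symptom on the Appendix 5 checklist and must be invited. The same patient scores 0/6 on the form and is not referred. Of the four local signs in superficial criterion c, the form keeps three and drops only erythema, which looks like an oversight.

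The survey is the planned route to examination once the week-1 visit is over, so it bears on how the primary outcome (superficial and deep SSI to day 30) is found for the rest of follow-up. Wound dehiscence is also a secondary outcome, and poor wound healing is a listed local adverse event of povidone-iodine. No survey question asks about wound separation.

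**Working it through.** The protocol states no figure on this point, so the check is a comparison of the two lists followed by a count.

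**Step 1. Symptoms and signs in Appendix 5 against survey item 3-5.**

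| Finding | Where in Appendix 5 | In item 3-5? |
|---|---|---|
| Pain or tenderness | superficial c, deep b | yes |
| Swelling | superficial c | yes |
| Heat | superficial c | yes |
| Erythema | superficial c | **no** |
| Pus | superficial a, deep a | yes |
| Fever | deep b | yes |
| Deliberate opening | superficial c, deep b | yes |
| Spontaneous dehiscence | deep b | **no** |

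There are eight findings, of which six are asked and 8 − 6 = 2 are not. The mismatch is confirmed.

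**Step 2. Can a patient meet a symptom-based criterion and still score 0/6?** Eight yes/no findings give 2^8 = 256 combinations. A score of 0/6 sets the six surveyed findings to absent, which leaves 2^2 = 4: neither omitted sign, erythema only, dehiscence only, or both. Testing these four:

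- Superficial a and deep a need pus. Pus is absent in all four.
- Superficial c needs a deliberately opened incision before erythema counts. Opening is absent in all four.
- Deep b needs fever or localized pain or tenderness alongside the dehiscence. Both are absent in all four.

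So 0 of the 4, and hence 0 of the 256, meet superficial a or c or deep a or b with a 0/6 score. The culture conditions in superficial c and deep b were ignored here; applying them would only remove cases, so the zero stands. The count assumes that patients report their symptoms fully. It also treats the sixth item as equivalent to the opening in superficial c, although the form limits it to openings before stitches are due out.

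**Step 3. Which criteria can coexist with 0/6?** Three require none of the listed symptoms: superficial b (organism from a specimen), superficial d (physician diagnosis) and deep c (gross or histopathologic examination, or imaging). Each needs the patient to reach a clinician, specimen or scan, which is what a 0/6 score does not arrange.

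**Step 4. When does the gate apply?** Patients are observed in hospital until discharge, and all are seen after week 1. Infections found at those points do not depend on the survey. The gap is confined to events arising, or becoming recognisable, after the week-1 visit.

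**Step 5. Dehiscence as an outcome.** Item 3-7 has a box for wound dehiscence, but only as a consequence of SSI, and item 3-8 has one for poor wound healing. Neither counts towards the referral score.

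**The case against.** A reader might infer that some SSIs will be scored 0/6 and never examined, and that the trial loses a calculable amount of power. The documents do not support either inference.

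- In Appendix 5 neither omitted sign is enough alone. Each counts only together with a finding that the survey does ask about, as Step 2 shows.
- The reporting instructions in Appendix 5 say that cellulitis by itself does not satisfy superficial criterion d, so many redness-only patients have no SSI to miss.
- Never examined is wrong. There is inpatient observation, a fixed visit for everyone and repeat surveys to day 30, so an infection that goes on to cause any of the six items is referred. Patients also hold a follow-up card and have free treatment of complications, so they can come in unprompted.
- A power loss would need a miss rate, and the documents give none. Applying an assumed rate to all SSIs would also count those found in hospital or at week 1, which never pass through the gate.

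It can also be said that the text asks only for a questionnaire guided by the CDC definitions, so a shortened lay survey is acceptable, and that a caller told of redness could still act on the broader rule in the text.

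The first four points stand, and they limit the finding to a possible, late and unquantified under-ascertainment. The last two do not remove the contradiction. A shortened survey is reasonable, but the text ties referral to the checklist itself, and the form tells the caller something different. Nor does the cellulitis exclusion justify leaving redness out, because a telephone call cannot separate simple cellulitis from an SSI that a physician would diagnose on examination.

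**Conclusion.** The contradiction between the Participant Timeline and item 3-5 is certain. Its effect is possible but not established. After the week-1 visit, SSIs that would rest on superficial b, superficial d or deep c, and wound dehiscence as a secondary outcome, may be under-ascertained when the only complaint is redness or a painless, afebrile separation. SSIs under superficial a or c or deep a or b would not be missed, given full symptom reporting.

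The size is unknown and probably small. Patients and outcome assessors are to be blinded and the same survey serves both arms, so any misses should be similar in each; no bias between arms is claimed. Severity: minor.

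**What to change.** Make the Participant Timeline rule and item 3-5 use one symptom list. The simplest way is to add two items to 3-5, redness at the surgical site and separation of the wound edges. The form's rule then becomes 1/8 or more for referral and 0/8 for a repeat survey, and the text should cite that list.

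The cost is two tick boxes, a changed denominator and the amendment paperwork. The one drawback is some extra clinic visits for redness that proves not to be SSI. No sample-size or analysis figure changes.

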Study Objective

To assess the efficacy of povidone-iodine wash before wound closure in preventing surgical site infections.

Trial Design

Superiority, parallel group randomized controlled trial, allocation 1:1

Methods

Study Setting

Operative theatres at Ain Shams University Hospitals

Inclusion Criteria

- Adult patients (≥ 18 years old)
- Open and minimally invasive surgeries
- Emergency (any unplanned admission) and elective (planned admission) surgical procedures
- Clean, Clean-Contaminated, Contaminated, Dirty wounds [22], (See appendix 1)
- Inclusion surgery list according to Current Procedural Terminology (CPT) National Healthcare Safety Network (NHSN) operative procedure code mapping [23] , List of included surgical procedures (See appendix 2)

Exclusion Criteria

- Povidone-iodine allergy
- Surgeries for infected wounds.
- Exclusion surgery list according to Current Procedural Terminology (CPT) National Healthcare Safety Network (NHSN) operative procedure code mapping, [23] List of excluded surgical procedures, (See appendix 3)

Intervention

- 10% povidone iodine wound wash before wound closure versus direct wound closure.
- Antibiotic prophylaxis will be administered according to local protocols.
- Wound dressing type and frequency will not differ between both groups.
- Diagnosed SSIs will be managed according to local antibiograms and management guidelines.

Outcomes

- Primary: Incidence of superficial and deep surgical site infection (SSI) within 30 days postoperatively
- Secondary:
 1. Post-operative morbidity and mortality by (Clavien-Dindo classification system) [24], (See appendix 4)
 2. Length of hospital stay
 3. Readmission and Reoperations related to surgical site infection
 4. Infectious complications (Sepsis, septic shock, multiple-organ dysfunction syndrome, wound dehiscence) [25-28]
 5. Microbiology culture and sensitivity results
 6. Local adverse events for povidone-iodine application (Local irritation, poor wound healing)
 7. Cost-analysis

Participant Timeline

Recruitment will start from day (18/09/2021) till sample size is reached.

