The allocation sequence will be made available to the OR head nurse in the form of sealed envelopes. The head nurse will provide the surgeons with closed opaque envelopes which will be opened by the nurse directly before wound closure. The head nurse will ensure that the envelopes are opened at wound closure and not before it. After the intervention/control is carried out, the random identifier will be noted down in the patient's operative data collection form. Following that, the nurse will tear the envelope and its contents.

Blinding

The patients and outcome assessors will be blinded. The details of which intervention was used will not be recorded in the regular patient records. The surgeons will be blinded till directly before wound closure, however, because of the nature of intervention, complete blinding of the surgeons would be impossible.

Data Collection Methods

Preoperative data collection will aim to collect baseline data about the recruited patients: patient identifiers, age, BMI, comorbidities including hypertension, diabetes, CKD, chronic liver disease, chronic heart failure, as well as any documented medication use and ASA score; through a standardized data collection form. All patients will be monitored by the doctors who will be responsible for filling their follow-up data till 30 days postoperatively (See appendix 6 for data collection forms).

Teams of four (surgeons or medical students) will be recruited to collect data from included surgical departments, each team collecting information over a two-week interval from all patients undergoing included surgical procedures in the department. Teams will then follow up with patients recruited in this allowed interval over the 30-day follow-up period, according to the methods described above.

We will obtain written informed consent from participants before surgery explaining the study procedures and the follow-up plans. All those who volunteer will be followed up in our clinics and provided carefree-of-cost.

Data Management

Package: R (latest available version)

Methods: Descriptive statistics will be presented as mean \pm SD for quantitative data. If the data is severely skewed/not normally distributed, median and IQR will be used. N & percentile will be used for qualitative data. Relevant statistical tests will be reported when applicable.

Statistical Methods

Suitable statistical tests will be used for data analysis.

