
3-3 *After surgery the patient was discharged to:
 
 Surgical ward  ICU (for how many days:.....)  Home
	
3-4-1 *What was the length of hospital stay after the surgical procedure?
 
..... days
 
3-4-2 *Was it extended due to wound infection related complications?
 
 Yes (specify:)  No
	
3-9 *Please specify patient grade according to Clavien-Dindo classification
 
 Grade I  Grade II  Grade III  Grade IIIa  Grade III b  Grade IV  Grade IV a  Grade IV b  Grade V
 
*Reason for choosing that grade:

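### Secondary outcome 4 is not limited to SSI, but the only form item naming its events records them only when attributed to SSI

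*Protocol*

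**What the plan says.** In the Protocol's Outcomes section, secondary outcome 4 reads "Infectious complications (Sepsis, septic shock, multiple-organ dysfunction syndrome, wound dehiscence". It is limited to infectious complications by its heading, but not to SSI. Outcome 3, directly above it, does carry an SSI limit: "Readmission and Reoperations related to surgical site infection".

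The Follow up page of the data collection form (Appendix 6) lists the same four events in item 3-7, under the question "Did the patient develop any of the following due to SSI". No other item names them as a set.

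Three other places bear on wound harm:
- Secondary outcome 6 is "Local adverse events for povidone-iodine application (Local irritation, poor wound healing".
- Item 3-8 asks "Was there any adverse effect of PVP-I application", with boxes for skin reaction, poor healing and other effects.
- Item 3-9 asks "Please specify patient grade according to Clavien-Dindo classification", with a reason for the grade and no SSI limit.

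The Blinding section states: "The patients and outcome assessors will be blinded".

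**The concern.** The form collects a narrower outcome than the Protocol defines, and the narrowing depends on a judgement about cause made after randomisation. This is a matter of data capture, not of analysis. If an event is not ticked because nobody attributes it to an SSI, no analysis plan can bring it back as that event.

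Two things are at stake. First, a patient with no diagnosed SSI cannot count for outcome 4, so its comparison between arms largely repeats the primary outcome, "Incidence of superficial and deep surgical site infection (SSI) within 30 days postoperatively", instead of adding to it. Second, the Protocol itself lists impaired healing as a possible effect of the wash. Dehiscence without infection is one way that effect could show, and no item records it in the same way in both arms.

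**Working it through.** **Setting the passages side by side**

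| Event | In outcome 4 as written? | Where the form can record it |
|---|---|---|
| Any of the four events, attributed to SSI | Yes | Item 3-7 |
| Sepsis, shock or organ dysfunction from another infection | Yes, an infectious complication | Not in 3-7; only indirectly through the grade and reason in 3-9 |
| Dehiscence without SSI | Named in the list, though the heading makes non-infected cases arguable | Not in 3-7; in 3-8 only if attributed to povidone-iodine; in 3-9 only through the grade and reason |

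Item 3-8 does not fill the gap. It asks for an effect of povidone-iodine, which a blinded assessor cannot judge and which has no meaning for a control patient. The adverse-event definition under Monitoring also requires a likely causal link to the intervention. Item 3-9 is free of attribution but does not name the events.

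**Illustration of size**

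The Protocol gives no rate for dehiscence or sepsis, so there is no stated figure to reproduce. Inputs:
- SSI risk s = 10% control and 5% wash, from the Sample Size section.
- Share of SSIs that dehisce, f = 10%, 20% or 30%, equal in both arms (assumed).
- Dehiscence among patients without SSI, q = 2% in both arms (assumed).
- All dehiscence in SSI patients is attributed to the SSI, and none in other patients (assumed).

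Formulas: recorded by item 3-7 = s × f; all dehiscence = s × f + (1 − s) × q.

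For f = 20%, control: recorded 0.10 × 0.20 = 2.0%; all 0.020 + 0.90 × 0.02 = 3.8%. Wash: recorded 0.05 × 0.20 = 1.0%; all 0.010 + 0.95 × 0.02 = 2.9%.

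| f | Recorded, control vs wash | RR | All, control vs wash | RR |
|---|---|---|---|---|
| 10% | 1.0% vs 0.5% | 0.50 | 2.8% vs 2.4% | 0.86 |
| 20% | 2.0% vs 1.0% | 0.50 | 3.8% vs 2.9% | 0.76 |
| 30% | 3.0% vs 1.5% | 0.50 | 4.8% vs 3.4% | 0.71 |

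The recorded RR is 0.05f / 0.10f = 0.50 for every f: it is the SSI ratio itself. The exaggeration is on the relative scale. The absolute differences are close: 0.5, 1.0 and 1.5 percentage points recorded, against 0.4, 0.9 and 1.4 for all dehiscence.

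**What a reversal would need**

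For equal totals, the wash-arm rate q must satisfy 0.05f + 0.95q = control total:
- f = 10%: (0.028 − 0.005) / 0.95 = 2.4%
- f = 20%: (0.038 − 0.010) / 0.95 = 2.9%
- f = 30%: (0.048 − 0.015) / 0.95 = 3.5%

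So the wash would have to raise non-SSI dehiscence from 2% to above 2.4-3.5%. At 4%, the all-dehiscence RR would be 0.043/0.028 = 1.54, 0.048/0.038 = 1.26 and 0.053/0.048 = 1.10, while item 3-7 would still show 0.50.

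**The case against.** The strongest reply is that item 3-7 may match what was meant. Outcome 4 is headed as infectious, so dehiscence without infection is not plainly inside it. SSI-related complications counted over all randomised patients are a legitimate outcome: preventing an SSI does prevent the sepsis it would have caused, and blinded assessors should make similar attribution errors in both arms. The Background defines SSI to include organ or space infection, so some sepsis ticked in item 3-7 could arise outside the superficial and deep infections of the primary outcome. Wound harm also has its own outcome 6 and items 3-8 and 3-9.

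Much of this stands. The place of non-infected dehiscence in outcome 4 is arguable, no differential bias between arms is shown, and the recorded events need not be a strict subset of the primary outcome. What does not fall away is that sepsis, shock or organ dysfunction from another infection fits outcome 4 as worded and is shut out by item 3-7. Outcome 3 shows that the SSI limit was written in where it was wanted.

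A reader might infer that harm to the wound without SSI is missed altogether. The documents do not support that: items 3-8 and 3-9 give partial cover, though it depends on attribution or does not name the event.

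A reader might also infer that the trial could show halved dehiscence when the true total is unchanged, say 4% in both arms with 20% of SSIs dehiscing. That leaves 4 − 2 = 2% against 4 − 1 = 3% outside SSI, or 2/90 = 2.2% against 3/95 = 3.2% of patients without SSI. It therefore assumes a rise of about 42% caused by the wash, for which the documents give no figure.

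**Conclusion.** The mismatch is in the text and holds: item 3-7 records a narrower, attribution-dependent version of outcome 4, and dehiscence without SSI has no item that is neutral between arms. The recorded contrast will tend to follow the SSI contrast. On the assumed rates, with equal non-SSI dehiscence, item 3-7 shows an RR of 0.50 where all dehiscence gives 0.71-0.86. Relative benefit is overstated, its direction is right, and the absolute difference hardly changes. A reversal is possible only if the wash adds non-SSI harm, which is an assumption and not something the documents show; the form as written would be poorly placed to detect it. The point affects a secondary outcome and the capture of harm. It does not touch the primary outcome or the sample size.

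**What to change.** Delete the limit to SSI from the wording of item 3-7, so that each of the four events within 30 days is recorded in both arms whatever its cause. Add a separate yes/no box for relation to SSI beside each event. Analyse the unrestricted events as outcome 4 and report the SSI-related subset alongside.

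The cost is one wording change, an added tick box and slightly more recording. Some recorded events will be ones that the wash cannot affect, which dilutes the contrast; the SSI-related subset keeps the narrower comparison available.

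Restating outcome 4 as SSI-related, as outcome 3 already is, would also remove the contradiction, but would leave non-SSI dehiscence without a neutral item. The attribution to povidone-iodine in item 3-8 is a separate weakness that this change does not repair.
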